5.2 EXCLUSION CRITERIA

- Severe psychiatric illness or mental deficiency sufficient to make making informed consent impossible
- Positive pregnancy test for women of childbearing age within 1 week or being actively lactating
- Immune mediated cytopenia responsive to the standard of care treatment
- Immune mediated cytopenia due to other autoimmune causes, such as systemic lupus erythrocytosis, chronic lymphocytic leukemia
- Patients who have previously received or currently take fostamatinib post-allogeneic transplant
- Non-immune mediated cytopenias. Etiologies including, but not limited to, cytopenias due to HIV infection, lymphoproliferative disorders, myelodysplasia/acute leukemia, drug-induced thrombocytopenia, thrombotic microangiopathies, acute bleeding, consumptive coagulopathy, fever, infections leading to cytopenia, medications induced cytopenias, thrombotic microangiopathies (disseminated intravascular coagulation), splenomegaly or hemophagocytic lymphohistiophagocytosis, relapse of primary disease.
- Patients with neutropenia, defined as absolute neutrophil count $\leq 1.0 \times 10^9/L$, will be excluded
- Uncontrolled hypertension (systolic blood pressure ≥ 140 mmHg or diastolic blood pressure ≥ 90 mmHg)

Abbreviated Title: Fostamatinib for post-transplant cytopenias

Version Date: 11/28/2023

- ALT or AST ≥ 3 times the upper limit of normal, or direct bilirubin ≥ 2 times the upper limit of normal
- Patients who have a history of medical disorders, that in the investigator's opinion, could affect the conduct of the study or the absorption, metabolism or excretion of the study drug are excluded.
- Patients with lymphoma/chronic lymphocytic leukemia, hepatitis, or HIV associated with ITP/wAIHA
- Patients with evidence of graft rejection (based on clinical suspicion supported by BM biopsy data and/or chimerism studies and/or MLR)
- Subjects recently treated (within 30 days) with cytokine-targeting biologics (anti-TNF, IL6) or B-cell or plasma-cell depleting antibody.
- Other cancers except that for which the transplant was done < 2 years before study entry, except non-melanoma skin cancer or carcinoma in situ of the uterine cervix or breast

5.3 INCLUSION OF VULNERABLE PARTICIPANTS

Adults unable to give consent are excluded from enrolling in the protocol. However, there is a possibility, though unlikely, that subjects could become decisionally impaired during the course of the study. Since there is a prospect of direct benefit from research participation, they may remain enrolled in the study as it is necessary for completion of the study objectives. If a subject loses the ability to consent due to an adverse event/serious adverse event, the subject will remain on study until that event resolves.

Legally Authorized Representative (LAR)

If subjects will remain in the study, a Legally Authorized Representative (LAR) will be identified and informed consent obtained from the LAR. Please see sections 10.1.1 and 10.1.4 for consent procedure.

Non-NIH Enrolling Sites

LAR will be assigned per institution requirements.

NIH Clinical Center

All subjects will be offered the opportunity to fill in their wishes for research and care, and assign a substitute decision maker on the "NIH Advance Directive for Health Care and Medical Research Participation" form so that another person can make decisions about their medical care in the event that they become incapacitated or cognitively impaired during the course of the study. The PI or AI will contact the NIH Ability to Consent Assessment Team (ACAT) for evaluation as needed for the following: an independent assessment of whether an individual has the capacity to provide consent; assistance in identifying and assessing an appropriate surrogate when indicated; and/or an assessment of the capacity to appoint a surrogate. For those subjects that become incapacitated and do not have pre-determined substitute decision maker, the procedures described in NIH HRPP Policy 403 for appointing a surrogate decision maker for adult subjects who are (a) decisionally impaired, and (b) who do not have a legal guardian or durable power of attorney, will be followed.

5.4 LIFESTYLE CONSIDERATIONS

Study participants should refrain from drinking alcohol.

Study participants and their partners should avoid pregnancy through abstinence or use of two highly effective forms of contraception until 1 month after last day of study drug.

Abbreviated Title: Fostamatinib for post-transplant cytopenias

Version Date: 11/28/2023

5.5 SCREEN FAILURES

Screen failures are defined as participants who consent to participate in the clinical trial but are not subsequently assigned to the study intervention or entered in the study because the participants did not meet the trial eligibility or withdrew consent. A minimal set of screen failure information is required to ensure transparent reporting of screen failure participants. Minimal information includes demography, screen failure details, eligibility criteria, and any serious adverse event (SAE).

Individuals who do not meet the criteria for participation in this trial (screen failure) may be rescreened once. The time interval between the initial screen and the rescreen should be ≥ 1 month. The re-screened participant will be assigned a new, unique participant number.

5.6 STRATEGIES FOR RECRUITMENT AND RETENTION

Non-NIH Enrolling Sites

Subjects will be recruited at each participating site in accordance with the site's recruitment strategy.

NIH Clinical Center

A Strategic Recruitment Plan (SRP) will be developed with the NHLBI Patient Recruitment Office (PRO) and ongoing regular meetings will be held with the PRO to ensure the study is meeting enrolment projections.

Referrals are expected primarily from BMT specialists; however, participants may be recruited via self-referral.

The recruitment strategies to be used for this study may include:

- Social media postings on Facebook and Twitter from NIH accounts – these may be paid or unpaid.
- Listings on official NIH websites to include:
 1. Clinicaltrials.gov
 2. Clinical Center Recruitment website with dedicated study page mirroring the patient recruitment flyer. Page links to CT.gov and/or Search the Studies.
 3. Clinical Center Research Studies (“Search the Studies”) website
- Clinical Center TV (CCTV) – these large TVs placed all around the NIH Clinical Center will rotate through various messages including one for this study.
- The AAMDS website and/or social media accounts (using IRB approved language, flyer, and/or social media language with photos.)
- Use of Clinical Center Office of Patient Recruitment Services (OPR) including OPR Listservs (*Email list of those interested in receiving study recruitment updates.*) (*Links to one of the above mentioned websites or pages.*) Includes the OPR Protocols and OPR Healthy Volunteers listservs and 3 NIH listservs (NIH Post back, NIH Clinical Fellows & NIH Study Volunteers),
- Craigslist & Research Match, NIH Newsletters
- An informational letter to physicians will be available for electronic (and hard copy as appropriate) distribution to local and other clinical specialist contacts.

In addition, to help recruit subjects for the study, a query within the Biomedical Translational Research Information System (BTRIS) will be run to help identify persons based on inclusion criteria (described in section 5.1). This query will be run bi-weekly where laboratory data is

Abbreviated Title: Fostamatinib for post-transplant cytopenias

Version Date: 11/28/2023

searched for adult subjects who have had allogenic transplant at the NIH within the past 10 years. The query process will be as follows:

- a) Platelet count: Thrombocytopenia, defined as average platelets count $<30 \times 10^9/L$ for 3 consecutive available readings at least 2 weeks apart
- b) Hemoglobin: defined as hemoglobin $\leq 9 \text{ g/dL}$ for 3 consecutive available readings at least 2 weeks apart
- c) Adults: Ages 18-75 years inclusive
- d) Subjects are ≥ 60 days post-allogeneic transplant

BTRIS will generate a list of subjects who meet the query criteria including their NIH medical record numbers. BTRIS will not include information on a subject's protocol or principal investigator. The following process will be used to obtain that information:

1. The "Protocol Information" tab within a subjects' Clinical Research Information System (CRIS) entry will be checked to determine the name of the Principal Investigator of that patient's applicable HSCT protocol.
2. The PI will be contacted by 000758 protocol personnel via secure email informing them that their patient may be eligible for our protocol. The email will ask the PI to consider sharing information about the protocol with their patient.
3. The PI will be provided with approved recruitment materials that they may share with their patient and provide the patient information about our study, inclusion criteria and study contact.

If recruitment projections/goals are not being met, additional strategies will be planned and implemented by the PRO.

5.6.1 Costs

By virtue of NHLBI sponsorship of clinical research protocols, enrolling sites qualify for Centers for Medicare and Medicaid Services (CMS) coverage of associated routine costs of medical care under the CMS Clinical Trial Policy (CTP). This policy is detailed at <https://www.cms.gov/Medicare/Coverage/ClinicalTrialPolicies/index.html>. According to this policy, CMS is explicitly authorized to provide payment for routine patient care costs and costs due to medical complications associated with participation in clinical trials.

5.6.2 Compensation

Study subjects will not be compensated for participation in this study.

6 STUDY INTERVENTION

6.1 STUDY INTERVENTIONS(S) ADMINISTRATION

6.1.1 Study Intervention Description

Eligible subjects will receive oral fostamatinib BID for 12 weeks. with the option to enroll on the extended access trial if deemed to be responsive at the end of the study.

Abbreviated Title: Fostamatinib for post-transplant cytopenias

Version Date: 11/28/2023

6.1.2 Dosing and Administration

Participants will receive fostamatinib 100 mg BID for 4 weeks.

6.1.2.1 Dose Continuation or Dose Escalation

On the 4-week evaluation,

a) if cytopenia improves (hemoglobin \geq 10 g/dL, platelets \geq 50 x 10^9 /L), patients will continue the same dose for a total of 12 weeks,

b) if refractory cytopenias persist (hemoglobin $<$ 10 g/dL, platelets $<$ 50 x 10^9 /L), the dose will be increased to 150 mg BID. Subjects with persistent (\geq 2 readings, 2 weeks apart) loss of hematologic response after week 5 can increase their dose to 150 mg BID until at end of the study on week 12.

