3.3 JUSTIFICATION FOR DOSE

The dose was based on prior FDA approval of fostamatinib use in chronic ITP and the ongoing phase III trial for wAIHA. The starting dose is 100 mg BID which can be increased to 150 mg BID if still refractory on the 4-week evaluation. Taper and dose modification are described in details in Section 5.1.2.3.

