6.1.2.3 Dose Modifications

Fostamatinib dose modification is recommended based on individual safety and tolerability. Management of some adverse reactions may require dose-interruption, reduction, or discontinuation.

A dose reduction schedule (DRS) is provided below. For example, if a patient is on the maximum (300mg total daily dose) at the time of an adverse reaction, the first dose reduction would be from 300mg/day to 200mg/day.

Dose Reduction Schedule (DRS)		
Total daily dose	Dosing Schedule	
	Morning	Evening
300mg	150mg	150mg
200mg	100mg	100mg
150mg	150mg ¹	---
100mg ²	100mg ¹	---

¹: Once daily fostamatinib should be taken in the morning.

²: If further dose reduction below 100mg/day is required, stop fostamatinib

Treatment may be delayed for a maximum of 14 days after holding the treatment for toxicities that develop and do not resolve as defined at 6.1.2.3 (neutropenia, LFT elevation, and diarrhea). The timing of subsequent lab and the study week are then adjusted to the study week that was stopped.

The recommended dose modification for adverse reactions are as the following:

	Recommended action
Hypertension Stage 1: systolic between 130-139 or diastolic between 80-89 mmHg	
 Initiate or increase dosage of antihypertensive medication for patients with increased cardiovascular risk, and adjust as needed until BP is controlled. If the BP target is not met after 8 weeks, reduce fostamatinib to next lower daily dose (refer to DRS). Consider cardiology consult

Stage 2: systolic at least 140 or diastolic at least 90 mmHg	
 Initiate or increase dosage of antihypertensive medication, and adjust as needed until BP is controlled. If BP remains 140/90 mmHg or higher for more than 8 weeks, reduce fostamatinib to next lower daily dose (refer to DRS). If BP remains 160/100 mmHg or higher for more than 4 weeks despite aggressive antihypertensive therapy, interrupt or discontinue fostamatinib. Consider cardiology consult

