- In the event that the subject is unable to tolerate 100 mg BID, the dose can be reduced to 150mg daily with re-assessment. If intolerable AEs with 150 mg daily, dose can be reduced to 100 mg daily. If unable to tolerate 100mg daily, patient will stop fostamatinib and will be off study. Intolerance is considered as any grade 3-4 AEs, probably or definitely related to fostamatinib, or any grade AE which, at the PI's discretion, appears to be distressing enough to the patient to lead to the drug's discontinuation. If the adverse events resolved and subject tolerates the dose reduction with no recurrence of AE, per PI discretion subject can be re-escalated one level at a time until back to the maximum tolerable dose.
- Causes of neutropenia in a AHCT recipient may include: infections such as cytomegalovirus infection, medication such as ganciclovir or other antibiotics, immunosuppressants such as mycophenolate or ruxolitinib, graft failure, relapse of primary disease. If neutropenia occurs, we will perform an extensively work up on the patient for the other causes stated above, and/or hold other potential culprit medications. We will give filgrastim to patients while doing the above work up. If no other causes are found, and the neutropenia does not recover, or recurs, with holding other medications, we will conclude that fostamatinib is contributing to the development of neutropenia.
- GvHD may mimic adverse events. If holding fostamatinib according to the DSR does not reverse the diarrhea, abdominal pain, transaminase elevation, AND there are no other causes (such as infection) identified, we will consider the cause of the adverse events to possibly be related to GVHD. In such circumstances, we will make every effort possible to perform biopsies of the involved organ systems to confirm the diagnosis of GvHD.

Dose adjustment for platelet counts and hemoglobin are as the following:

Thrombocytosis	
PLT $\geq 200 \times 10^9 /L$ to $\leq 400 \times 10^9 /L$ at any time	
 • Decrease the dose to the next lower dose level. Wait 2 weeks to assess the effects of this and any subsequent dose adjustments.
PLT $> 400 \times 10^9 /L$ at any time	
 • Stop fostamatinib. Increase the frequency of platelet monitoring to twice weekly. • Once the platelet count is $< 150 \times 10^9 /L$, resume fostamatinib at the next lower dose level

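### Escalation to 150 mg BID carries no condition on current dose, tolerability or strong CYP3A4-inhibitor use, and inhibitor users have no stated maximum after week 5

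*Combined protocol and SAP*

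**What the plan says.** **General rule.** Section 6.1.2 sets the starting regimen: "Participants will receive fostamatinib 100 mg BID for 4 weeks". Under 6.1.2.1, if the cytopenia is still refractory at week 4, "the dose will be increased to 150 mg BID". Sections 1.1, 1.2 and 3.1 repeat this as an instruction (*will*). Section 3.3 is softer: "The starting dose is 100 mg BID which can be increased to 150 mg BID if still refractory on the 4-week evaluation". After week 5, 6.1.2.1 adds that subjects with persistent "loss of hematologic response after week 5 can increase their dose to 150 mg BID"; sections 1.2 and 3.1 repeat this optional step.

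**Dose reductions.** Section 6.1.2.3 opens with "Fostamatinib dose modification is recommended based on individual safety and tolerability" and gives a ladder of 300, 200, 150 and 100 mg/day. For intolerance it says "In the event that the subject is unable to tolerate 100 mg BID, the dose can be reduced to 150mg daily with re-assessment", with 100 mg daily below that. The way back up is conditional: "If the adverse events resolved and subject tolerates the dose reduction with no recurrence of AE", then "per PI discretion subject can be re-escalated one level at a time until back to the maximum tolerable dose". The liver table has a similar one-level provision at the PI's discretion.

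**Count rules.** The same section lowers the dose by one level, followed by a two-week wait, whenever platelets are 200 to 400 x 10^9/L or hemoglobin is 13 to 15 g/dL.

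**Strong CYP3A4 inhibitors.** Sections 2.3.1 and 6.1.2.4 start subjects who cannot be switched at 150 mg daily. They allow 100 mg BID at week 4 if the subject is refractory and tolerating treatment. Neither section mentions loss of response after week 5.

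**The concern.** Section 6.1.2.1 names a fixed target, the maximum dose, rather than a step up from wherever the subject stands. It refers to neither 6.1.2.3 nor 6.1.2.4. Three situations follow.

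1. A strong-inhibitor user who loses response after week 5 has no specific rule. The subject started low because 2.3.1 expects higher R406 exposure and possibly more adverse reactions, yet the only applicable text permits the same maximum as for a subject on no inhibitor.
2. A subject reduced after an adverse event and still refractory at week 4 falls under two rules that disagree, and no sentence ranks them.
3. The count rules are not limited to the lineage that was low at entry. A subject with single-lineage cytopenia can therefore meet a decrease rule and an increase rule at one visit.

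At stake are dosing safety and consistency across up to four sites. Section 10.9.1 counts any departure from the approved protocol as a deviation, so an investigator who sensibly withholds the week-4 increase could be recorded as deviating.

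**Working it through.** The plan gives no figure on this point to reproduce. The check compares the rules and counts steps on the 6.1.2.3 ladder. All ratios are of labelled daily dose, not of exposure or risk; the documents do not quantify the rise in R406.

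**Step 1. Who can be on a reduced dose by week 4.** Liver events, grade 3 or higher diarrhea, neutropenia and intolerance can each lower the dose within four weeks. The hypertension reductions wait eight weeks, so they play no part at week 4. Reaching 100 mg/day takes two reductions from 200.

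**Step 2. Rules side by side (mg/day).**

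| Situation | More specific text | 6.1.2.1 read literally | Ratio |
|---|---|---|---|
| Reduced to 150 after an AE, refractory at week 4 | 200, one level at most | 300, two levels | 300/200 = 1.5 |
| Reduced to 100 after an AE, refractory at week 4 | 150, one level at most | 300, three levels | 300/150 = 2.0 |
| On 200 at week 4, low platelets only, platelets < 50 and hemoglobin 13 to 15 | 150, one level down | 300, one level up | 300/150 = 2.0 |
| Strong inhibitor, loss of response after week 5 | None; highest dose named is 200 | 300 permitted | 300/200 = 1.5 |

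A subject on 200 mg/day who tolerates it moves one level to 300, and no conflict arises. The third row has a mirror case: an anemia-only subject with hemoglobin < 10 and platelets 200 to 400. Both versions assume that refractoriness is judged on the lineage low at entry.

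**Step 3. Strong-inhibitor users at week 4.** Section 6.1.2.4 gives them a specific target (100 mg BID) with a tolerability condition, so the general rule does not reach them at that visit. The gap opens only afterwards. A user who had responded by week 4 is still on 150 mg daily, so the permitted rise would be 300/150 = 2.0 times the current dose in one move.

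**Step 4. Time at the higher dose.** For the AE-reduced group: week 12 − week 4 = up to 8 weeks. For strong-inhibitor users, assume both readings fall after week 5 and at scheduled visits:
- weeks 6 and 8: (84 − 56)/7 = 4.0 weeks left;
- the same pair, each 4 days early (days 38 and 52): (84 − 52)/7 = 4.6 weeks;
- weeks 8 and 10: (84 − 70)/7 = 2.0 weeks.

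**Step 5. Effect on the design.** The two-stage rule in 9.1 (stop if ≤ 1 of 11; reject if > 4 of 20) depends only on those numbers and the assumed rates. An exact binomial calculation gives power 0.860 at 35%, matching the stated 86%, and type 1 error 0.040 at 10%, within 0.05. The dosing text enters neither.

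**The case against.** The best defence is that nobody would read 6.1.2.1 in isolation. It follows directly on the 100 mg BID regimen, so its step is naturally from 100 to 150 mg BID. Section 3.3 says the dose *can* be raised, and its next sentence points to a section 5.1.2.3 for dose modification; that section does not exist, so 6.1.2.3 is evidently meant. Section 3.1 describes the week-4 visit as the first point at which the dose may be adjusted if needed, and 7.1 also sends the reader to 6.1.2.3. This stands. It shows that 6.1.2.3 is intended to govern AE-reduced subjects, though it is not a precedence clause and leaves the *will* in four sections.

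For strong-inhibitor users, the defence is that the group is narrow, the step is optional, little time remains, and 100 mg BID may be read as the top of their ladder. The narrowness stands. The last point is an inference: no sentence states a maximum, and the general rule excludes nobody.

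Three stronger readings are tempting and should be resisted:
- A reader might infer that the protocol deliberately orders subjects with recent toxicity to the maximum dose. The context above does not support that.
- A reader might treat the count-rule clash as a breach of the one-level rule. That rule covers re-escalation after adverse events; the count reductions have no re-escalation rule at all. The two-week wait also argues against raising the dose at the same visit.
- A reader might take the ratios as exposure multiples. They are not.

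**Conclusion.** The point holds as a minor safety wording correction.

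- **Strong-inhibitor users after week 5** are the clearest gap: no text caps them below 300 mg/day, against a highest named dose of 200, for about 2 to 4.6 weeks.
- **AE-reduced subjects at week 4:** the mandatory wording contradicts 6.1.2.3 (300 against 200 or 150 mg/day). The intended order is evident but unstated, and most investigators would probably follow 6.1.2.3.
- **Count rules:** opposite instructions at one visit are possible in single-lineage cytopenia. This is a separate defect of scope.

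The number of subjects affected cannot be estimated from the documents and is probably small. Sample size, power and type 1 error do not change.

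**What to change.** In 6.1.2.1 and its repeats in 1.1, 1.2 and 3.1, state that:

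1. escalation to 150 mg BID, at week 4 or later, applies only to subjects currently tolerating 100 mg BID and not on a strong CYP3A4 inhibitor;
2. subjects reduced after an adverse event re-escalate only under 6.1.2.3;
3. strong-inhibitor users stay at or below 100 mg BID for all 12 weeks, unless the clinical team states another maximum.

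In 6.1.2.3, limit the platelet and hemoglobin upper-limit reductions to the lineage low at entry, and give a one-level route back up after such a reduction. Without that route, count-reduced subjects could not be re-escalated once the 150 mg BID step is restricted.

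Classify voriconazole once. Section 2.3.1 names it among the strong inhibitors of concern, while Appendix A, to which 6.1.2.4 refers, lists it as moderate.

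The cost is a wording amendment to those sections, with no extra patients, visits or procedures. The downside is slightly lower dose intensity in a few subjects.
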